3.2. Randomization

Not applicable.

3.3. Control of Type I Error

All statistical analyses are exploratory in nature. Unless otherwise specified, all CIs provided will be at the 95% confidence level.

3.4. Sample Size Considerations

3.4.1. Sample Size in Part 1

The primary objective of Part 1 of the study is to determine the PAD or the MTD of INCAGN01949. The total number of subjects will depend on the number of dose levels tested before the MTD or PAD is established. Approximately 18 to 36 subjects (6 subjects per dose level for 6 dose levels) will be included based on the dose escalation. Dose escalation will follow the 3 + 3 design algorithm. Based on this algorithm, a minimum of 3 evaluable subjects will be enrolled in each cohort beginning with Cohort 1 (7 mg; starting dose) and a maximum of 6 evaluable subjects for each cohort. The probability of declaring a dose cohort as safe for various DLT rates in the 3 + 3 and the safety expansion is summarized in [Table 2](#).

Table 2: Probability of Dose Escalation by DLT Rate for 3 + 3 Design and Safety Expansion

True DLT Rate	Probability of Declaring Dose Cohort as Safe	
	3 + 3 Design	In Both 3 + 3 Design and Safety Expansion
10%	90.6%	85.8%
20%	70.9%	52.3%
30%	49.4%	22.9%
40%	30.9%	7.2%
50%	17.2%	1.5%
60%	8.2%	0.2%

For example, if the true DLT rate is 50% at a given dose level, there is a 17.2% chance that the dose would be escalated. Further, if the true DLT rate is 20%, there is a 70.9% chance that the dose would be escalated. If the MTD is not determined at the highest dose level tested during the study, then the MTD is at or above the highest dose level. The MTD is below the lowest dose level of INCAGN01949 if Cohort 1 is not well-tolerated. The PAD may be used in lieu of the MTD and/or prescribed doses may need to be altered in order to determine the MTD.

[figure not shown]
Part 1 of the study may also include safety expansion cohorts evaluating doses and schedules equivalent to or lower than the highest dose levels determined to be safe and/or doses determined to be pharmacologically active. Each safety expansion cohort will enroll 9 evaluable subjects (up to 36 subjects). If < 3 of 9 evaluable subjects experience a DLT, the cohort will be deemed safe. If more than 1 safety expansion cohort is deemed safe, then the recommended dose will be determined in conjunction with the investigators and sponsor based on all available safety, PK,
[redacted] results.

3.4.2. Sample Size in Part 2

Part 2 of the study will further evaluate the safety, tolerability, preliminary efficacy, PK, and pharmacologic activity of the recommended dose of INCAGN01949. The sample size for each tumor type will be guided by the Simon 2-stage design ([Simon 1989](#)). Let $P_0 = 5\%$ denote a clinically insignificant response rate for all tumor types. In order to determine whether the target response rate (25%) is likely, an initial number of evaluable subjects (9 subjects) treated at the

MTD or PAD and schedule of INCAGN01949 will be enrolled in a cohort (Stage 1). If there is no response for the cohort, it will be concluded that the true response rate is unlikely to be greater than or equal to the target rate, and no more subjects will be enrolled in that tumor type in Stage 2. Due to replacement of subjects for biopsy analysis, additional subjects may be enrolled for the biopsy evaluable population; however, the first 9 evaluable subjects in each cohort will be used for early stopping at Stage 1. In the tumor types in which at least 1 response among the Stage 1 subjects is observed, 8 additional evaluable subjects will be treated in Stage 2 to estimate the response rate. At the end of Stage 2, if ≤ 2 subjects have responded among the evaluable subjects, the drug will be declared nonpromising for that tumor type. In other words, after the study is finished, if there is a sufficient number of responses in the 2 stages combined, the study compound is considered promising; otherwise it is considered nonpromising. The detailed calculation is based on a 1-sided Type I error of 0.05 and power of 80% for each of the tumor types. [Figure 2](#) shows the power to reject the null hypothesis for various response rates.

Figure 2: Power and Type I Error for Simon 2-Stage Design for Various Response Rates

4. DATA HANDLING DEFINITIONS AND CONVENTIONS

4.1. Scheduled Study Evaluations and Study Periods

4.1.1. Day 1

Day 1 is the date that the first dose of study drug (INCAGN01949) is administered to the subjects.

4.1.2. Study Day

If a visit/reporting date is on or after Day 1, then the study day at the visit/reporting date will be calculated as

$$\text{Day \#} = (\text{Visit/Reporting Date} - \text{Day 1 date} + 1).$$

If the visit/reporting date is before Day 1, then the study day at the visit/reporting date will be calculated as

$$\text{Day \#} = (\text{Visit/Reporting Date} - \text{Day 1 date}).$$

A study day of -1 indicates 1 day before Day 1.

4.1.3. Baseline Value

Baseline is the last nonmissing measurement obtained before the first administration of INCAGN01949.

When scheduled assessments and unscheduled assessments occur on the same day and time of the assessment or time of first dose is not available, use the following convention to determine baseline:

- If both a scheduled and an unscheduled visit are available on the day of the first dose and the time is missing, use the scheduled assessment as baseline.
- If all scheduled assessments are missing on the day of the first dose and an unscheduled assessment is available, use the unscheduled assessment as baseline.

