5.4.8. Management of Infusion Reactions

[Table 6](#) shows treatment guidelines for subjects who experience an infusion reaction associated with study drug administrative procedures. Signs and symptoms usually develop during or shortly after drug infusion and generally resolve completely within 24 hours of completion of infusion.

Table 6: INCAGN01949 Infusion Reaction Treatment Guidelines

CTCAE Grade	Treatment	Premedication at Subsequent Dose Administration

Grade 1: Mild reaction; infusion interruption not indicated; intervention not indicated.
	
Increase monitoring of vital signs as medically indicated until the subject is deemed medically stable in the opinion of the investigator.
	
None.

Grade 2: Requires infusion interruption but responds promptly to symptomatic treatment (eg, antihistamines, NSAIDs, narcotics, IV fluids); prophylactic medications indicated for ≤ 24 hours.
	
Stop infusion and monitor symptoms. Additional appropriate medical therapy may include but is not limited to the following:
 
 • IV fluids • Antihistamines • NSAIDs • Acetaminophen • Narcotics 
Increase monitoring of vital signs as medically indicated until the subject is deemed medically stable in the opinion of the investigator.
 
If symptoms resolve within 1 hour of stopping drug infusion, the infusion may be restarted at 50% of the original infusion rate. Otherwise, dose administration will be interrupted until symptoms resolve, and the subject should be premedicated for the next scheduled dose.
 
Subjects who develop Grade 2 toxicity despite adequate premedication should be permanently discontinued from further study drug administration.
	
Subject may be premedicated 1.5 h (± 30 min) before infusion with the following:
 
 • Diphenhydramine 50 mg orally (or equivalent dose of antihistamine). • Acetaminophen 500-1000 mg orally (or equivalent dose of antipyretic).

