^c On Day 1 of the first 4 cycles (C1D1, C2D1, C3D1, and C4D1), subjects will be required to stay at the study site for safety observation for up to 4 hours postinfusion. It is recommended that the subject does not leave the site for any reason during the safety observation period. During the safety observation period, vital signs (blood pressure, pulse, respiratory rate, and body temperature) will be assessed every 60 minutes ± 10 minutes (eg, 1 hour postinfusion, 2 hours postinfusion, 3 hours postinfusion, and 4 hours postinfusion). Subjects will also be assessed for the onset of acute AEs.

^d Laboratory assessments may also be required on additional visit days as described in Table 8 and Table 9.

- ^e All 12-lead ECGs will be performed with the subject in a recumbent or semirecumbent position after 5 minutes of rest and should not be performed within 15 minutes after a blood collection.
- ^f In the event that a single QTc is > 470 milliseconds, the subject may enroll if the average QTc for the 3 ECGs is < 470 milliseconds.
- ^g **Triplicate ECG measurements are required at screening, C1D1 (in conjunction with PK samples), and C6D1 (in conjunction with PK samples).** Other ECGs only need to be performed in triplicate if there has been a QT prolongation on study or if the ECG shows a clinically significant abnormality not present at baseline. Triplicate ECG measurements should be performed predose and within 1 hour postdose. Measurements should be taken in triplicate (separated by 5 minutes ± 5 minutes).
- ^h A 12-lead ECG should be performed on Day 1 of every other cycle after C2 (eg, C4, C6, C8, C10).
- ⁱ The initial tumor imaging will be performed within 28 days before the first dose of study drug. Scans performed as part of routine clinical management are acceptable for use as the screening scan if they are of diagnostic quality and performed within 28 days before the first dose of study drug. The same imaging technique should be used for a subject throughout the study. Local reading (investigator assessment with site radiology reading) will be used to determine eligibility and for subject management.

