^b If liver chemistry tests are abnormal (eg, change in grade from baseline), then liver chemistry monitoring should increase to once per week until resolved to baseline. Liver chemistry does not need to be monitored once per week indefinitely for persistent low grade abnormalities. Appropriate liver chemistry monitoring intervals should be discussed with the medical monitor for those circumstances.

^c Screening laboratory tests must be performed within 7 days of Cycle 1 Day 1. If performed more than 7 days before Cycle 1 Day 1, then the tests must be repeated and eligibility confirmed before study drug administration on Cycle 1 Day 1.

^d Only required to be performed at Cycle 1 Day 1 if the screening assessment was not performed within 7 days.

^e A serum pregnancy test will be required for all women of childbearing potential during screening and must be performed within 72 hours before the first dose of study drug.

^f Urine pregnancy tests will be conducted as medically indicated or per country-specific requirements.

^g CA-125 should be performed at Cycle 1 Day 1 and with the radiographic tumor assessment (± 7 days).

Table 9: Schedule of Pharmacokinetic and Pharmacodynamic Assessments

Visit Day (Range)	Protocol Section	Timing of Assessment	Screening	Treatment											Post-Treatment	
				C1			C2	C3	C4	C6			C7	C8 and C12	EOT	Safety Follow-Up Visit 1
				D1	D2	D7	D1	D1	D1	D1	D2	D7	D1	D1		
Evaluation/Window			Day -28 to -1			± 1 day	± 1 day	± 3 days	± 3 days	± 3 days		± 1 day	± 3 days	± 3 days		30 days (+ 7 days)
Pharmacokinetics Assessments^a																
Serum sample for PK ^b	7.9	Table 13		X	X	X	X	X	X	X	X	X	X	X		

^a All PK [redacted] assessments will be performed by a central laboratory. Details regarding PK [redacted] samples including specimen handling, processing, and shipping will be outlined in the laboratory manual.

^b Adjustments to the time of PK [redacted] blood sampling postdose may be made based on emerging PK data; however, no additional postdose timepoints will be used, and the maximum scheduled timepoints will be not greater than 6 hours postdose on the day of infusion.

[Large redacted block of text]

Table 10: Local Laboratory Tests: Required Analytes

Serum Chemistries	Hematology	Urinalysis	Hepatitis Screening	Coagulation

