8.4. Vital Signs

Values at each scheduled visit, change, and percentage change from baseline for vital signs, including systolic blood pressure, diastolic blood pressure, pulse, respiratory rate, body temperature, and weight will be summarized descriptively. Change and percentage change from baseline will be calculated using the last nonmissing value before first dose of study drug (Day 1) as the baseline value.

Criteria for clinically notable vital sign abnormalities are defined in [Table 6](#). The abnormal values for subjects exhibiting clinically notable vital sign abnormalities will be listed along with their assigned treatment group. Alert vital signs are defined as an absolute value outside the defined range and percentage change $> 25\%$. The abnormal values for subjects exhibiting alert vital sign abnormalities will be listed.

Table 6: Criteria for Clinically Notable Vital Sign Abnormalities

Parameter	High Threshold	Low Threshold
Systolic blood pressure	> 155 mmHg	< 85 mmHg
Diastolic blood pressure	> 100 mmHg	< 40 mmHg
Pulse	> 100 bpm	< 45 bpm
Temperature	> 38°C	< 35.5°C
Respiratory rate	> 24/min	< 8/min

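### SAP 4.1.3 lets an untimed unscheduled Day 1 value become baseline without evidence that it was predose, and for laboratory tests it conflicts with SAP 8.3.2

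*SAP*

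**What the plan says.** SAP 4.1.3 opens with a clear definition: "Baseline is the last nonmissing measurement obtained before the first administration of INCAGN01949". It then gives a convention for this situation: "When scheduled assessments and unscheduled assessments occur on the same day and time of the assessment or time of first dose is not available". The first bullet prefers the scheduled Day 1 assessment. The second reads "If all scheduled assessments are missing on the day of the first dose and an unscheduled assessment is available, use the unscheduled assessment" as baseline. Neither bullet requires the chosen value to be predose, and neither falls back to screening.

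The rules for each data type differ:

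- **Laboratory tests.** SAP 8.3.1 refers to 4.1.3. SAP 8.3.2 instead draws on values collected before the first dose, ranks scheduled above unscheduled, and takes the last record in the highest rank.
- **Vital signs.** SAP 8.4 calculates change "using the last nonmissing value before first dose of study drug (Day 1) as the baseline value".
- **ECG.** SAP 8.5 fixes baseline as the mean of the preinfusion triplicate on Cycle 1 Day 1.

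The protocol affects which values exist on Day 1. Under Table 8, footnote d, most Cycle 1 Day 1 laboratory tests are "Only required to be performed at Cycle 1 Day 1 if the screening assessment was not performed within 7 days". Table 7, footnote c, schedules postinfusion sets for the first four cycles: "During the safety observation period, vital signs (blood pressure, pulse, respiratory rate, and body temperature) will be assessed every 60 minutes". Table 6 (Section 5.4.8) says of infusion reactions: "Increase monitoring of vital signs as medically indicated until the subject is deemed medically stable in the opinion of the investigator".

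**The concern.** Once timing is unknown, the general definition cannot be applied and the two bullets decide. They resolve the doubt as if the value were predose. The SAP does the opposite elsewhere: an AE counts as treatment-emergent unless it clearly is not (8.2.1), and a medication counts as concomitant unless it clearly is not (4.2.1.2).

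A postdose value used as baseline distorts every later comparison for that subject. The value itself leaves the postbaseline grade tables, later values of the same grade show no shift, and a recovery is displayed as a change from baseline. This is a first-in-human dose-escalation study that observes subjects for acute effects after the first infusion, so baselines on that day should not be left to an assumption.

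**Working it through.** The plan states no figure to reproduce. The check traces the rule through each data type and then works two examples. The grades and pressures are assumed for illustration; the limits are those of SAP 8.4 and Table 6 of the SAP.

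**Can the trigger arise?**

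- Laboratory tests: yes, by design. If screening tests fall within 7 days, no scheduled Cycle 1 Day 1 sample is needed. Protocol 7.6.5 allows extra tests when clinically indicated, and Protocol 6.6 allows unscheduled visits at any time. One untimed unscheduled Day 1 sample then meets the second bullet, if a waived test is read as missing.
- Vital signs, second bullet: only if every scheduled Cycle 1 Day 1 set is absent, including the hourly ones.
- Vital signs, first bullet: this needs untimed scheduled and unscheduled readings on Day 1. The scheduled readings then include postinfusion sets (for example at 1, 2, 3 and 4 hours), and the bullet does not say which to use.
- AEs and DLTs: they do not use this baseline.
- ECG: 8.5 overrides 4.1.3.

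**Laboratory example.** Assume a scheduled screening value of Grade 0, no scheduled Day 1 sample, one untimed unscheduled Day 1 value of Grade 3 that was in truth postdose, and a later worst value of Grade 3.

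| Rule followed | Baseline | Shift shown |
|---|---|---|
| 4.1.3 through 8.3.1 | Grade 3 (unscheduled Day 1) | 3 to 3, no worsening |
| 8.3.2 | Grade 0 (scheduled screening) | 0 to 3 |

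If later values return to Grade 0, the first rule shows 3 to 0. The second shows 0 to 3 only if the Day 1 value is treated as postbaseline, which 8.3.2 does not settle.

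**Vital-sign example.** Assume screening systolic pressure of 120 mmHg and an untimed unscheduled Day 1 reading of 80 mmHg, in truth postdose, with no scheduled Day 1 set entered. A value is notable below 85 or above 155 mmHg. An alert also needs more than 25% change from baseline, taken here as a change in either direction.

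- Against 120: (80 − 120)/120 = −33%. The reading is below 85, so it is notable and an alert.
- With 80 as baseline, a later 80: (80 − 80)/80 = 0%. Notable, but not an alert.
- With 80 as baseline, a later 120: (120 − 80)/80 = +50%. Within range, but shown as a large rise.

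The reading of 80 would still be listed as notable, because SAP 8.4 applies absolute limits and does not restrict that listing to postbaseline values. What changes is the alert status and the change-from-baseline figures.

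**The case against.** The strongest reply is that the bullets are only a tie-break under an opening sentence that already requires a predose value, and that other sections close most of the gap. Protocol 7.6.5 requires Day 1 laboratory samples before dosing. SAP 8.3.2 would select the scheduled screening value. SAP 8.4 repeats the predose condition for vital signs, and the nominal timepoint of a postinfusion set can identify it as postdose.

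Much of this stands, and it is why the point is small. It does not remove the point. A sample drawn because of a reaction to the infusion cannot have been predose. Sections 8.3.1 and 8.3.2 point to different rules and nothing says which governs. A predose condition in 8.4 cannot be applied when the time is unknown, and 4.1.3 does not tell the programmer to use the nominal timepoint.

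A reader might infer three stronger claims that the documents do not support:

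- *Unscheduled Day 1 values are usually postinfusion.* The documents give no such share. Unscheduled visits may occur at any time, and laboratory samples have a documented predose requirement.
- *Drug effects drop out of the safety summaries.* The primary endpoint is AE frequency, duration and severity. It does not use this baseline, AEs of doubtful timing default to treatment-emergent, and infusion reactions have their own listing (2.6.14).
- *The error always makes the drug look safer.* The +50% above shows that a false baseline can also exaggerate a later change. If the untimed value was truly predose, 4.1.3 handles it correctly. Declaring all such values postbaseline would then count a pre-existing abnormality as a drug effect.

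**Conclusion.** The point holds in a limited form and is minor. SAP 4.1.3 has no predose condition for untimed unscheduled Day 1 values, and for laboratory tests it gives a different baseline from 8.3.2. For vital signs it does not separate the scheduled predose set from the postinfusion sets. For an affected subject, the errors fall in laboratory shift and change-from-baseline tables and in vital-sign change and alert outputs. The error arises only if a time is missing and the chosen value was in fact postdose. How often that happens cannot be computed from the documents; it is probably rare. The conflict between 8.3.1 and 8.3.2 is a matter of wording and does not depend on that frequency.

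**What to change.** In SAP 4.1.3, replace the two bullets with one rule: a Day 1 value may serve as baseline only if its recorded time, or its nominal timepoint or visit label, shows that it was taken before the first infusion; otherwise use the last value before Day 1. Align 8.3.1 with 8.3.2 so that one laboratory baseline rule governs. List untimed unscheduled Day 1 values with their timing flagged as unknown, rather than assigning them to either side of the dose by default.

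This changes SAP wording only. The cost is that a few baselines will be older, up to the 28-day screening window. For laboratory tests where the Day 1 sample was waived, the screening value is at most 7 days old.

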4.1.4. Handling of Missing and Incomplete Data

In general, values for missing data will not be imputed unless methods for handling missing data are specified in this section or relevant sections.

Partial disease/cancer diagnosis date will be handled as follows:

- If only the day is missing, then the imputed day will be the first of the month.
- If both the month and day are missing, then the imputed day and month will be 01 JAN.
- No imputation will be done if the date is completely missing.

Missing or partial date of last dose will be handled as follows:

- If only the day is missing, then the imputed date of the last dose will be the earlier date of the first day of the month or the date that the subject discontinued treatment.
- Otherwise, the date that the subject discontinued treatment will be used as the date of the last dose.

For relevant efficacy endpoints, partial death date will be imputed as follows:

- If mmYYYY for the last contact date = mmYYYY for the death date, then the death date will be set to the day after the last contact date.
- If mmYYYY for the last contact date < mmYYYY for the death date, then the death date will be set to the first day of the death month.
- Otherwise, the partial death date will not be imputed.

For prior and concomitant medications:

The start/stop dates recorded in the CRF by the investigator and his or her research staff will be used to identify when a concomitant medication was taken during the study. Any missing start date must be queried for resolution. Unresolved missing start dates will be handled as follows:

- If the date is completely missing, the medication will be considered both prior and concomitant.
- If only the day is missing, and the last day of the month is before the first dose date on Day 1, then the concomitant medication will be considered as starting before Day 1, and the incomplete date will be imputed as the last day of the month.
- If only the day is missing, and the first day of the month is after the first dose date on Day 1, then the concomitant medication will be considered as starting after Day 1, and the incomplete date will be imputed as the first day of the month.
- If only the day is missing, and the month is equal to the month of the first dose date on Day 1, then the incomplete date will be imputed as the first day of the month.
- If both the month and day are missing, and the last day of the year is before the first dose date on Day 1, then the concomitant medication will be considered as starting before Day 1, and the incomplete date will be imputed as if it is the last day of the year. Otherwise, the incomplete date will be imputed as if it is the first day of the year.

